9.4.1 General Considerations

As recruitment to the study has been terminated and the final sample size is too low to perform originally planned analysis, analyses will consist of descriptive summaries and figures of safety data for the double-blind placebo-controlled period (Part A) and the openlabel periods (Parts C and D) as well as select patient listings of demographic and baseline characteristics, safety and key efficacy data. No statistical analyses or hypothesis testing will be performed.

All available data will be included in data presentations, regardless of use of rescue therapy, restricted medications for EG/EGE or treatment discontinuation.

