9.4.2 Efficacy

All available (from Part A and Part C) peak eosinophil count (eos/hpf) data will be listed by patient including whether patients achieved a histological response at available visits, defined as ≤ 6 eosinophils/hpf in the stomach and/or, ≤ 15 eosinophils/hpf in the duodenum, as applicable based on disease area involvement at enrollment.

All available (from Parts A and C) SAGED score data will be listed by patient including individual abdominal pain, nausea, bloating, early satiety and loss of appetite severity item scores and the bi-weekly SAGED score calculated as the 14-day mean of the daily sum of the item scores.

Listings of other efficacy endpoints may be produced as required including all available data from Parts A, C, and D. Individual patient data may be presented graphically as appropriate.

Available efficacy data collected in relation to EG-REFs, EoD-REFs, PGI-S/C, CGI-S/C will be listed by patient (from the point of protocol amendment onwards only PGI-C data is collected during Part D but data already collected from patients in Part C will be included as available).

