## 3.3 General Considerations

The primary efficacy analyses will be based on the double-blind placebo-controlled first 24 weeks of the study (DB period). In this part of the study all efficacy analyses will use the full analysis set (FAS) as defined in Section 3.2, and patients will be analyzed according to their randomized treatment, following the Intent-to-Treat (ITT) principle.

A composite estimand strategy will be used for the primary analyses of endpoints at Week 24 whereby any patients who have required rescue corticosteroids, use of a restricted medication, or discontinued IP during the first 24 weeks will be considered as treatment failures at Week 24.

A review of all concomitant medications during the study will be performed prior to database lock to identify events to be considered as treatment failure in these analyses, whereby only medications considered likely to have a meaningful impact on EG/EGE outcomes would be considered intercurrent events. This could include addition of a new therapy or an increase in previously stable background medications to treat EG/EGE. For the histologic response rate endpoint, patients with these intercurrent events prior to Week 24 will be considered non-responders at Week 24; for the change from baseline in SAGED score at Week 24 endpoint, as well as other change from baseline continuous endpoints, any patients experiencing the described intercurrent events will have their worst observation (including baseline value) prior to or at the intercurrent event carried forward to Week 24.

All patients who prematurely discontinue from IP, use restricted medications, or have any changes to background therapies for EG/EGE as described above are asked to come in for all visits until they complete the overall study duration. Therefore, sensitivity analyses can be performed to assess the robustness of the efficacy results to these estimand approaches and missing data assumptions as described in individual endpoint analysis methods in Section 4.2.

The statistical analyses of the DB period are designed to compare both efficacy and safety of benralizumab to placebo, while the OLE period is designed to evaluate the long-term safety and tolerability and persistence of effect of benralizumab in this patient population. Details regarding primary and key secondary estimands with additional details including sensitivity analyses are provided in Section 4.2.

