# 4.2 Endpoint Analyses

This section covers details related to the endpoint analyses such as primary, secondary, other endpoints including sensitivity and supportive analyses. The primary and key secondary endpoints will be analysed following the hierarchical order based on the overall population and within the subgroup of patients with gastric disease (with or without intestinal involvement), respectively. See Section 3.3.4 for details.

For part B analyses, alpha level will follow the instruction shown in Figure 2 for primary and key secondary endpoints. For other endpoints not included in the testing hierarchy, alpha will be 0.05 and all p-values will be considered nominal. For part A analyses, alpha level will be 0.1.

A composite approach will be used for all the responder analyses whereby any patients who have intercurrent events of rescue use, restricted medication use, or randomized treatment discontinuation during the analyses period will be considered as non-responders.

A composite approach will be used for all the continuous analyses, where worst observation prior to or at the intercurrent events of rescue use, restricted medication use, or randomized treatment discontinuation will be carried forward (WOCF). If a participant has had only improvements since baseline this will result in the baseline value being carried forwards.

For the descriptive summaries of each endpoint, the number and percentage of subjects with imputation based on composite approach will be displayed. The descriptive summaries will summarise the results once the imputations have been made.

Table 5 Primary, key secondary efficacy and main safety estimands						
Statistical category	Endpoint	Population	Intercurrent event strategy	Population level summary (analysis)	Details in section	
Objective 1: Part A/B: To compare the effect of benralizumab 30 mg every 4 weeks (Q4W) with placebo on histologic signs and gastrointestinal symptoms in patients with eosinophilic gastritis and/or gastroenteritis						
Primary/MCP	Proportion of patients with a histologic response at Week 24	FAS	Treatment discontinuation - composite (treated as non-responder) Required rescue corticosteroids or use of a restricted medication a - composite (treated as non-responder)	Odds ratio and difference in proportions from stratified CMH test at Week 24.	Section 4.2.1	

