#### 8 ADDENDUM

Protocol Version 5 (Amendment 4) was issued on March 28, 2023, after the decision to close recruitment to the study early. The amendment rationale was to fulfil a commitment to participants, from when they enrolled in the trial, of open-label access to benrazilumab following double-blind treatment.

Patients that completed Part A prior to approval of amendment 4 could choose to continue to Part C, an extended open-label benralizumab treatment period. Patients in Part A and Part C, after protocol amendment approval in their respective country, will be given the option at their next clinic visit of withdrawing from the study or moving on to Part D and receiving 6 months of open-label benralizumab Q4W dosing. Patients will not complete their current treatment period. Patients who have discontinued IP during Part A are not eligible to enter Part C or D.

Enrollment was terminated after enrollment of 34 participants, of which 12 were randomized. The figure below illustrates the current study design described above.

Figure 4 Study Design Flow Chart

Q4W: every fourth week; R: reference visit number of weeks (ie, visit prior to approval of Amendment 4); EoT: end of treatment; FU: follow-up.

Given the original sample size of the study will no longer be recruited and the study will be terminated, the analysis plan for the study was updated. The amended analysis plan will now consist of descriptive summaries of safety data and select patient listings of baseline characteristics, safety data, and key efficacy data for the double-blind placebo-controlled period (part A) and the open-label period (Parts C and D). Details on the descriptive summaries can be found below in Table 11.

Principles outlined in the main SAP document related to these descriptive summaries below will apply i.e. definition of periods for safety summaries. Other analyses described in the main SAP will no longer be implemented given the small final sample size limiting the ability to assess the original study objectives.

Table 11 List of summaries for the final analyses

Summaries	Period Period	Population	Format
Subject disposition	DB + OLE	All patients analysis set	Table
Duration of exposure	DB	Safety analysis set	Table
Duration of exposure	OLE	Open-label benralizumab analysis set	Table
Adverse events in any category	DB	Safety analysis set	Table
Adverse events in any category	OLE	Open-label benralizumab analysis set	Table

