Serious adverse events – key subject information	DB	Safety analysis set	Table
Adverse events causing discontinuation of study treatment – key subject information	DB + OLE	Safety analysis set	Table
Haematology and clinical chemistry, baseline to minimum/maximum value post-baseline, on-treatment	DB	Safety analysis set	Table
Haematology and clinical chemistry, post-baseline values outside central laboratory reference ranges – key subject information	DB	Safety analysis set	Table
Subjects discontinued from the study	DB + OLE	All patients analysis set	Listing
Subjects completing the study	DB + OLE	All randomized subjects	Listing
Demographic and baseline characteristics		All randomized subjects	Listing

Additional demography		All randomized subjects	Listing
EG/EGE Disease History	DB	Full analysis set	Listing
Respiratory Disease History	DB	Full analysis set	Listing
Concomitant medication during study treatment	DB + OLE	Full analysis set	Listing
Peak eosinophil count (eos/hpf)	DB + OLE	Full analysis set	Listing
PGI-S and PGI-C	DB + OLE	Full analysis set	Listing
CGI-S and CGI-C	DB + OLE	Full analysis set	Listing
Symptom Assessment for Gastrointestinal Eosinophilic Diseases (SAGED) score	DB + OLE	Full analysis set	Listing
EG-REFS Score	DB + OLE	Full analysis set	Listing
EoD-REFS Score	DB + OLE	Full analysis set	Listing
EoE-REFS Score	DB + OLE	Full analysis set	Listing
Adverse events	DB + OLE	Safety analysis set	Listing
Laboratory data – Haematology	DB + OLE	Safety analysis set	Listing
Laboratory data – Chemistry	DB + OLE	Safety analysis set	Listing
Laboratory data – Urinalysis	DB + OLE	Safety analysis set	Listing
Vital signs	DB + OLE	Safety analysis set	Listing
SAGED score change from baseline in mean value by time point, WOCF, line plot	DB	Full analysis subset	Figure

AstraZeneca 2-Oct-2023

SAGED score components mean	DB	Full analysis subset	Figure
value at Week 24, WOCF, line			
plot			

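### Both SAGED figures in SAP Table 11 use worst observation carried forward, although amended Protocol 9.4.1 says all available data are presented regardless of the events that trigger it

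*SAP*

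**What the plan says.** **Protocol, as amended.** Section 9.4.1 replaces the planned analyses with descriptive output and sets one rule for what goes into it: "All available data will be included in data presentations, regardless of use of rescue therapy, restricted medications for EG/EGE or treatment discontinuation". It assigns summaries and figures to safety data and listings to key efficacy data. Section 9.4.2 lists SAGED scores by patient and adds: "Individual patient data may be presented graphically as appropriate".

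**SAP addendum (Section 8).** The text describes the output as "descriptive summaries of safety data and select patient listings of baseline characteristics, safety data, and key efficacy data". Table 11 nevertheless ends with two SAGED figures for the double-blind period. One is "SAGED score change from baseline in mean value by time point, WOCF, line plot"; the other shows SAGED component means at Week 24 and is also labelled WOCF. The SAGED listing in the same table carries no such label. On the rest of the SAP, the addendum says: "Principles outlined in the main SAP document related to these descriptive summaries below will apply". It then illustrates this with the period definitions for safety summaries and drops the other main-SAP analyses.

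**Main SAP.** Section 3.3 says that patients with an intercurrent event "will have their worst observation (including baseline value) prior to or at the intercurrent event carried forward to Week 24". Section 4.2 names the events: "worst observation prior to or at the intercurrent events of rescue use, restricted medication use, or randomized treatment discontinuation will be carried forward (WOCF"). It adds that a patient who has only improved has the baseline value carried forward. Section 2 declares no changes from the protocol's planned analyses.

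**The concern.** The three events that trigger WOCF in the SAP are the three events that the amended protocol says must not affect what is presented. If Table 11 is followed, the plotted means can contain substituted values where the protocol promises observed ones.

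The substitution is not reliably conservative. Baseline is one of the candidate values, so an imputed change is never an improvement. A worsening after the event, on the other hand, is replaced by an earlier and better score. An arm mean can therefore look worse or better than the data.

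Only 12 patients were randomised, so one or two substitutions would be visible. A mean plot by arm is also easily read as the efficacy picture of the study, whatever the listings show.

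**Working it through.** The plan gives no number on this point to reproduce. The check is a comparison of texts, followed by an illustration of size.

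**1. Same events, opposite rules.**
- Rescue: Protocol 9.4.1 includes the data; SAP 4.2 carries the worst value forward.
- Restricted medication: Protocol 9.4.1 includes the data; SAP 4.2 carries the worst value forward.
- Discontinuation of treatment: Protocol 9.4.1 includes the data; SAP 4.2 carries the worst value forward.

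**2. Is Table 11 leftover text?** No. The addendum cites Amendment 4, issued 28 March 2023, and the page with the figures is dated 2 October 2023. It is the operative list of final output.

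**3. Does the main-SAP rule carry over?** The carry-over sentence is narrow, since its only named example is safety periods. There are two branches:
- The rule carries over: the figures contradict Protocol 9.4.1.
- It does not: WOCF in Table 11 has no definition.

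Either way the specification needs correcting. Even on the first branch, Section 3.3 defines a carry-forward to Week 24, so its use at earlier time points in the first figure is not spelled out.

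**4. Can there be observed scores to replace?** Yes, after rescue or restricted medication, because neither in itself stops the daily diary, and SAP 3.3 asks such patients to attend all visits. After discontinuation there is less: Protocol 7.1.2.1 has the diary device returned at the discontinuation visit, within about 4 weeks of the last dose. After that visit WOCF would fill gaps rather than overwrite data.

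**5. Size, illustration only.** The documents give 12 patients randomised 1:1. The arm size n, the true change and the number imputed k are assumptions.

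Shift of the arm mean = k × (WOCF change − observed change) / n, where a negative change is an improvement on the 0 to 50 scale.
- Improver, observed −10, WOCF 0, k = 1: 10/6 = 1.67 points towards no change at n = 6; 10/5 = 2.00 at n = 5; 10/7 = 1.43 at n = 7.
- At n = 6 with an improvement of 5 or 15 points: 5/6 = 0.83 or 15/6 = 2.50.
- Two 10-point improvers at n = 6: 20/6 = 3.33.
- Worsener, baseline 20, worst score up to the event 22, later score 30: WOCF plots +2 instead of +10, so the mean looks 8/6 = 1.33 points better at n = 6 (8/5 = 1.60 at n = 5; 8/7 = 1.14 at n = 7).
- k = 0: no shift.

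**6. Exits caused by the amendment.** The addendum lets Part A patients withdraw or move to Part D at their next visit, without completing the current period. SAP 4.2 is triggered by stopping randomised treatment. The SAP does not say whether either exit counts.

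**The case against.** The best defence is that little depends on these figures. Protocol 9.1 and 9.4.1 rule out hypothesis testing, the report is synoptic, and the SAGED listing shows every observed score. If SAP 4.2 carries over in full, the number imputed would be displayed as well. Protocol 9.4 already requires deviations to be reported in the study report. All of this stands, and it limits the size of the point. It does not reconcile the two rules.

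Some stronger readings are tempting, but the documents do not support them.
- **The mean plots are themselves a breach of the protocol.** Protocol 9.4.1 and 9.4.2 foresee safety figures, efficacy listings and individual graphs, but they do not forbid other displays. The contradiction lies in the WOCF label.
- **A move to Part D is simply missing data, and only withdrawal is a trigger.** Protocol 7.1.2.1 separates discontinuing the product from entering Part D, but for eligibility; it does not define the trigger. Both exits end randomised treatment early, so a literal reading of SAP 4.2 could catch both. The position is unspecified.
- **The population label 'Full analysis subset' means the full analysis set.** It appears only in the two figure rows and may be a slip or a real restriction. It should be defined, not assumed.
- **The double-blind period cannot be determined for patients who moved early.** SAP 3.3.1.1 still ties its end to Week 24, but SAP 4.6.2.1 ends double-blind adverse events on the day before the first open-label dose, and the addendum treats Parts C and D as open-label. This is stale wording, as is SAP Section 2.

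**Conclusion.** The inconsistency is real and should be fixed. Table 11 asks for WOCF in both SAGED figures, amended Protocol 9.4.1 asks for all available data regardless of the same events, and no departure is declared. The conclusion rests on WOCF in Table 11 having its main-SAP meaning; without that meaning the term is undefined, which also needs repair.

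The impact is confined to two descriptive figures. A reader might infer that the trial's efficacy conclusions are biased, but the plan draws no inferential conclusion and keeps the observed listing. The number of patients affected is not given: it may be zero and cannot exceed 12. The shift of about 1.7 points for one 10-point improver assumes 6 patients per arm and is not an estimate of what occurred.

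**What to change.** In SAP Table 11, plot observed bi-weekly SAGED scores in the double-blind period with n at each time point, for the total and for the components, or plot individual profiles as Protocol 9.4.2 allows.

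If a WOCF version is kept:
- show it only beside the observed-data figure, with the number of patients imputed;
- declare it as a departure from Protocol 9.4.1;
- state that leaving Part A because of Amendment 4, by transfer to Part D or by the withdrawal offered at that visit, is an administrative end of double-blind follow-up and not a WOCF trigger.

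Editorial only: define 'Full analysis subset', remove the Week 24 anchor from the double-blind period definition in SAP 3.3.1.1, and update SAP Section 2.

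The cost is two figure specifications and a few sentences, with no new data. Fewer patients will contribute at late weeks, which the displayed n makes plain.
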